Treatment:	Patients eligible for initial treatment with KRYSTEXXA 8 mg by intravenous (i.v.) infusion every 2 weeks will be offered enrollment into the observational study for a year. Serum uric acid (SUA) levels will be monitored prior to infusion and therapy will be discontinued if levels increase above 6 mg/dL on two consecutive measurements. If the SUA is noted to be above 6 mg/dL the sponsor suggests that a repeat SUA should be drawn when the result is noted to confirm, and if the 2 consecutive levels are noted to be above 6 mg/dL then it is advised to discontinue therapy.
Study duration:	Approximately 63 weeks, including 51 weeks of treatment and 12 weeks of follow-up.
• Selection criteria	
Inclusion criteria:
 

• Adult patients (age <math>\geq</math> 18 years) with chronic gout refractory to conventional therapy, defined as patients who have failed to normalize SUA and whose signs and symptoms are inadequately controlled with xanthine oxidase inhibitors at the maximum medically appropriate dose, or for whom these drugs are contraindicated.

• Patients who have made the decision, along with their treating physician, to begin treatment with KRYSTEXXA.

• Patients who are willing and able to give informed consent and adhere to visit/protocol schedules (informed consent must be given before the first study procedure is performed).

 
Exclusion criteria:
 

• Glucose-6-phosphate dehydrogenase (G6PD) deficiency

• Non-compensated congestive heart failure

• Pregnancy or breast feeding

• Prior treatment with pegloticase or another recombinant uricase

• Known allergy to urate oxidase

• Prior treatment or concomitant therapy with a polyethylene glycol (PEG)-conjugated drug

• Recipient of an investigational drug within 4 weeks prior to study drug administration or plans to take an investigational agent during the study

Investigational drug:	None
Reference therapy:	KRYSTEXXA® (pegloticase) 8 mg i.v. every 2 weeks

---

Efficacy criteria:	Normalization of SUA to < 6 mg/dL  Decrease in the number of swollen joints and the number of tender joints  Decrease in the frequency of gout flares  Reduction in the number of tophi

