Safety criteria:	IRs, anaphylaxis, and immune complex-related adverse events, serious adverse events and adverse event profile, including gout flares
Statistical methods:	
Descriptive statistics will be employed to summarize the proportion of responders, where a responder is defined as a patient whose SUA values were < 6 mg/dL at their final 2 consecutive study visits. Descriptive statistics will be provided for the number of swollen joints and tender joints at baseline, 6 months and 12 months or Early Discontinuation; for changes in numbers of gout flares based on patient reported history at 6-week intervals for Months 1-3 and 3-month intervals thereafter; and for change in the number of tophi at 6 months (Visit 13) and 12 months (Visit 26) or Early Discontinuation.
 
It is anticipated that there may be a considerable number of study patients who will drop out of the study. The sponsor will make every effort to identify the reason(s) for dropout before reaching the primary safety endpoint. For the analysis of each efficacy endpoint, various sensitivity analyses will be performed under different assumptions of potentially informative dropouts. For continuous efficacy variables, sensitivity analyses will be performed using standard mixed-effect model repeated measure (MMRM) methods. All the analyses will be summarized using 95% confidence interval estimates. The resulting summarized statistics for efficacy will be compared to those reported from the pre-approval phase 3 studies.
 
Adverse events will be summarized by presenting the proportion of patients having any adverse event (AE), overall and by body system, and by event as defined by the Medical Dictionary for Regulatory Activities (MedDRA) preferred term. Separate summary tables will be provided for IRs, anaphylaxis AEs, and immune complex-related AEs.
 
For each type of the primary safety endpoints, one event, at most, will be counted per patient. The 95% (exact) confidence interval estimates for each type of safety endpoint will be reported for the rate of incidence both at the administrative interim analysis, for evaluating the feasibility of the study, and at the final analysis. The following hypothesis will be specifically tested: the rate of IRs seen in the phase 3 studies will be reduced in this study by monitoring SUA prior to infusions and

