discontinuing therapy in patients if levels increase to above 6 mg/dL, particularly when 2 consecutive levels above 6 mg/dL are observed. With at least 500 patients enrolled with 1 year follow-up, the power of detecting a 26% IR rate (the observed value from the pre-approval phase 3 studies) against 13% is at least 90%. The rate of IRs reported during the study will be reported and compared descriptively to the rates observed in the pre-approval phase 3 studies.

There is no planned interim analysis. However, the number of enrolled patients will be reassessed approximately 2 years after the first patient is enrolled. This data will be utilized to make a prediction concerning the future enrollment profile. The enrollment goal may be adjusted depending on the drop-out rate such that approximately 500 patients will complete the 1 year treatment period.

**Assessments:** Baseline samples for identification of antibodies to pegloticase and to PEG, and determination of complement markers (complement component 3 [C3] and complement component 4 [C4]) and tryptase levels. Antibody samples at End-of-Study and at 3-month intervals during follow-up after discontinuation of treatment.

Review of concurrent medications, co-morbidities, and compliance with premedication regimes for gout flares.

Determination of SUA before each infusion.

Recording of drug, dose and timing of IR prophylactic medications.

Recording of infusion start and finish times, sodium chloride diluent used and the total volume infused.

Swollen joint and tender joint counts, and number of tophi to be assessed at baseline, 6 months (Visit 13) and 12 months (Visit 26) or Early Discontinuation.

Flares:

- At baseline, document the history of gout flares from the previous 6 months
- Documentation of the occurrence and duration of any gout flares experienced while the patient is participating in the study

IRs and anaphylaxis:

- Documentation of signs and symptoms and onset time in relation to the initiation of the KRYSTEXXA infusion, and treatment, if any
- Follow-up laboratory assessments may include the collection of samples for analysis of antibodies to pegloticase and PEG, anti-pegloticase IgE, C3, C4, and tryptase levels.

Immune complex disease:

- Clinical investigation of a presumptive immune complex disease (as per clinical practice) and of complement markers (C3, C4) will be pursued.

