### **1.2.2 Safety Assessments in Clinical Studies of KRYSTEXXA**

The most commonly reported serious adverse reactions from the pre-marketing controlled clinical trials in patients treated with KRYSTEXXA 8 mg every 2 weeks were gout flare, IR, and anaphylaxis.

Gout flares were more frequent during the first 3 months of treatment (74% in KRYSTEXXA-treated patients vs. 51% in placebo-treated patients), and seemed to decrease over the next 3 months (41% KRYSTEXXA vs. 67% placebo). An increase in gout flares is frequently observed upon initiation of anti-hyperuremic therapy. Thus, all patients in these studies received non-steroidal anti-inflammatory drugs (NSAID) or colchicine or both for at least 7 days as gout flare prophylaxis before beginning KRYSTEXXA; patients continued on this regimen for the 6-month treatment duration.

All patients in Phase 3 clinical trials were pre-treated with an oral antihistamine (fexofenadine, 60 mg by mouth [po], the night before and morning of the infusion), i.v. corticosteroid (200 mg hydrocortisone i.v.) and acetaminophen (1000 mg po) before the infusion to prevent anaphylaxis and IRs. Nevertheless, IRs were reported in 26% of patients treated with KRYSTEXXA 8 mg every 2 weeks compared to 5% of patients treated with placebo. Manifestations of IRs included urticaria, dyspnea, chest discomfort, chest pain, erythema, and pruritus. Approximately 3% of IRs occurred with the first dose, and most (91%) occurred during the infusion rather than after it was completed.

None of the IRs which occurred in the pegloticase studies was categorized as anaphylaxis by the investigators who enrolled subjects in the Phase 2, Phase 3, or open-label extension studies. The US FDA performed a retrospective analysis of the IRs to assess for anaphylaxis, using modified National Institute of Allergy and Infectious Disease/Food Allergy and Anaphylaxis Network (NIAID/FAAN) diagnostic criteria (Sampson et al, 2006). Using their analysis, the frequency of anaphylaxis was 6.5% in all patients treated with KRYSTEXXA 8 mg every 2 week. During randomized, placebo-controlled studies, the frequency was 5% compared to none with placebo. An independent immunologist commissioned by the sponsor to review the data based strictly upon the NIAID/FAAN clinical criteria for anaphylaxis determined the overall rate in the clinical studies to be 2.4%.

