### **3.5.1 Screening Procedures**

Prior to entry into the protocol, the nature and risks of the study must be reviewed with each patient. Each patient or each patient's legal representative must be given the opportunity to read the Institutional Review Board's (IRB) approved informed consent (IC) form and ask questions. After all questions raised by a potential participant are answered, and before any protocol-specified screening procedures are initiated, each patient or each patient's legal representative must sign and date the consent form. A copy of the signed and dated IC form must be provided to the patient.

After IC is obtained, a 6-digit patient number will be assigned. The first three digits of each patient number will represent the site and the last three will be unique for each patient at each site. Potential patients will be screened to determine if they satisfy all inclusion and exclusion criteria. All screening procedures must be completed prior to dosing. Specified CRF/eCRF pages to report basic demographic information and reason(s) for exclusion must be completed for all patients who signed an informed consent form, but never received KRYSTEXXA.

The following evaluations will be performed on each patient and results recorded in the medical record and CRF/eCRF:

- Informed consent (process must be documented in the medical record)
- Medical history – include all clinically significant medical problems within the past 5 years, but excluding gout history which will be separately documented
- Gout history and symptom severity
  - Documentation of the contraindication to or the failure of conventional therapy at the maximum medically appropriate dose
  - Number of gout flares in the last 6 months, and most recent occurrence
  - Assessment of tophi and gouty arthritis, including a count of the total number of palpable subcutaneous and subperiosteal tophi, if accessible
  - The number of tender joints and swollen joints
  - Documentation of the history of gout-related kidney disease
- Physical examination (including but not limited to dermatological, head and neck, chest and cardiac, abdominal, musculoskeletal, and nervous system examination)
- Vital signs and height and body weight
- Obtain a blood sample for analysis of SUA
- Obtain a blood sample for G6PD testing

- Review concomitant medications

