#### **3.5.4 Early Discontinuation from the Study**

Patients who completely discontinue their participation in the study and do not consent to be followed for the full year are to return 4 weeks (+/- 5 days) after their final infusion of KRYSTEXXA in order to undergo early discontinuation study procedures. These procedures include essentially the same procedures as Visit 26, but without SUA and adding only blood samples for antibodies and the final instruction to patients:

- Inquire and assess for AEs, gout flares and changes in concomitant medications since previous study visit
- Determine and record the reason for the early discontinuation of the patient

- Complete physical exam, reviewing same body systems as at screening visit
- Measure blood pressure, heart rate and temperature
- Collect blood samples for antibodies to pegloticase or PEG
- Perform swollen joint and tender joint count
- Perform a count of the total number of palpable subcutaneous and subperiosteal tophi, if accessible
- Instruct patients on post-study anti-hyperuricemic therapy as appropriate

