##### **3.6.2.2 Gout flares**

The occurrence and duration of gout flares will be reported throughout the study. The number of gout flares will be assessed by 6-week intervals for the first 3 months, and by 3-month intervals through the end-of-study.

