#### **6.1.5 Efficacy Evaluation**

One efficacy endpoint in this study is normalization of SUA to < 6 mg/dL. Descriptive statistics will be employed to summarize the proportion of responders, where a responder is defined as a patient whose SUA values were < 6 mg/dL at their final 2 consecutive study visits. Summary statistics will be provided for the number of swollen joints and tender joints at baseline, 6 months

(Visit 13) and 12 months (Visit 26) or Early Discontinuation; for changes in numbers of gout flares based on patient reported history at 6-week intervals for Months 1-3 and 3-month intervals thereafter; and for elimination of tophi, i.e., the number of patients with a reported tophus resolution at 6 months (Visit 13) and 12 months (Visit 26) or Early Discontinuation.

It is anticipated that there may be a considerable number of study patients who will drop out of the study. The sponsor will make every effort to identify the reason(s) for dropout before reaching the primary safety endpoint. For the analysis of each efficacy endpoint, various sensitivity analyses will be performed under different assumptions of potentially informative dropouts. For example, in the responder analysis, one analysis will be based on the ITT population with various imputation methods for missing values at the end. Analyses will also be performed assuming all “informative” dropouts are non-responders. For continuous efficacy variables, sensitivity analyses will be performed using standard mixed-effect model repeated measure (MMRM) methods. All the analyses will be summarized using 95% confidence interval estimates. The resulting summarized statistics for efficacy will be compared to those reported from the pre-approval Phase 3 studies.

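### Gout flare change is planned as a difference in counts over windows of 6 weeks, 3 months and 6 months, with no common time unit or observed-time denominator

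*Protocol*

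**What the plan says.** The synopsis lists, among four efficacy criteria, "Decrease in the frequency of gout flares". The planned summary is worded differently. The synopsis (Statistical methods) provides descriptive statistics "for changes in numbers of gout flares based on patient reported history at 6-week intervals" in Months 1-3 and by quarter afterwards, and section 6.1.5 repeats this: "changes in numbers of gout flares based on patient reported history at 6-week intervals for Months 1-3 and 3-month intervals thereafter". Section 3.6.2.2 gives the same windows: "The number of gout flares will be assessed by 6-week intervals for the first 3 months, and by 3-month intervals through the end-of-study".

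The only pre-treatment flare measure is a six-month history. The synopsis (Assessments) has "At baseline, document the history of gout flares from the previous 6 months", and section 3.5.1 has "Number of gout flares in the last 6 months, and most recent occurrence".

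No section says which period the change is measured from, in what time unit, or how incomplete observation enters. Section 6.1 leaves further detail to the SAP, and the SAP contains no flare analysis. Section 6.1.5 expects considerable dropout. Under section 3.5.4, patients who decline further follow-up "are to return 4 weeks (+/- 5 days) after their final infusion of KRYSTEXXA" for their exit procedures.

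Section 6.1.5 also plans to compare the efficacy results with those reported from Phase 3. The Phase 3 flare figures given in the protocol (section 1.2.2) are percentages: "74% in KRYSTEXXA-treated patients vs. 51% in placebo-treated patients" in the first three months, then 41% against 67% in the next three.

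**The concern.** A count grows with the time over which it is taken. Here the reference window is six months and no single on-study window has that length. The on-study window also roughly doubles after Month 3, which is where section 1.2.2 reports that flares began to decline in Phase 3. A literal difference in counts therefore mixes any real change in flare frequency with a change in window length. Against baseline, the mixing favours the drug. Across the Month 3 switch, it works against the drug.

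Early leavers add a second source of mixing, because their last window is observed only in part. The sensitivity analyses in section 6.1.5 (imputation, treating informative dropouts as non-responders, MMRM) concern missing outcomes. They do not supply a denominator for a count.

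At stake is the interpretability of one of the four efficacy criteria. The primary objective concerns infusion reactions, anaphylaxis and immune complex-related events, and is not affected.

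**Working it through.** The documents state no expected flare rate or power for this endpoint, so there is no figure of the plan's own to reproduce. The check asks what a literal count comparison shows when the flare rate does not change.

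**Inputs**
- Baseline window: 6 months (synopsis, section 3.5.1).
- On-study windows: 6 weeks in Months 1-3, then 3 months (sections 3.6.2.2 and 6.1.5).
- Weeks per quarter: 12, as section 3.5.3 converts 3 months for follow-up visits, or 13 by the calendar (assumption). Six months is then 24 or 26 weeks.
- Exit visit: 28 days after the final infusion, with a tolerance of 5 days (section 3.5.4).

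**Unequal windows, constant rate.** Expected count = rate × window length, so the ratio of two counts is the ratio of their windows.

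| Comparison | 12-week quarter | 13-week quarter | Apparent change |
|---|---|---|---|
| 6-week window vs baseline | 6/24 = 0.250 | 6/26 = 0.231 | 75% or 77% fall |
| 3-month window vs baseline | 12/24 = 0.500 | 13/26 = 0.500 | 50% fall |
| 6-week to 3-month window | 12/6 = 2.00 | 13/6 = 2.17 | 2.0- or 2.2-fold rise |

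For example, a patient with 6 flares in 26 weeks and no change in rate would be expected to have 6 × 6/26 = 1.4 flares in a 6-week window and 6 × 13/26 = 3.0 in a 13-week window.

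**Shortened last window.** Take an 84-day window and an exit visit exactly 28 days after the final infusion. The apparent change against a fully observed window of the same length, at an unchanged rate, is:
- final infusion on day 0 of the window: 28/84 observed, a 67% fall;
- day 28: 56/84 observed, a 33% fall;
- day 56: 84/84 observed, no fall;
- day 70: this window is complete and the next has 14/84 observed, an 83% fall in that next window.

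The effect can therefore be nil or large. Section 3.5.6 also allows the visit to take place sooner. The documents do not say how many patients will be affected.

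**After the change.** Dividing each count by its observed time returns the rate itself. A constant rate then gives a 0% change from baseline and a ratio of 1.0 between 6-week and 3-month windows, whether or not the window is complete. Equal-length windows observed in full show no artefact even as raw counts.

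**The case against.** The strongest reply is that the plan never tells anyone to subtract a six-month count from a six-week count. The criterion speaks of frequency, the six-month history is the evident comparator, and a competent analyst would scale it. This is partly right. A reader might infer that the reported results will be biased by 50 to 77%, and the documents do not support that, because the figures apply only if raw counts are compared. But the planned summary is stated in numbers, and neither document sets out the scaling.

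Three further inferences also go too far.
- That the Phase 3 comparison cannot be made for flares. The Phase 3 reports are not among the documents and may contain counts or rates. All that can be said is that section 1.2.2 gives percentages, which a change in counts does not match.
- That section 1.2.2 shows how large a real fall would be masked. Turning percentages into rates needs a flare distribution and complete observation, and the documents give neither.
- That flares after early discontinuation go uncollected because Schedule 2 in Appendix 3 has no flare row, while Schedule 1 has one. Section 3.5.3, including its additional follow-up visits, requires flare assessment, and section 3.7.1 captures each confirmed flare as part of safety. This is a mismatch between table and text, with no data loss shown.

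**Conclusion.** The point stands as a minor one. The flare summary is defined in counts over windows of three different lengths, for a criterion expressed as frequency, with no time unit or observed-time denominator in either document. Taken literally, an unchanged rate would appear as a 75-77% fall (6-week window against baseline), a 50% fall (3-month window against baseline) or a 2.0- to 2.2-fold rise (6-week to 3-month window). These figures assume a constant rate, complete windows and 12 or 13 weeks to the quarter. For early leavers no single figure can be given, since the effect depends on when the final infusion falls. The endpoint is secondary and descriptive. Confidence is high that the definition is missing. Whether raw counts would in fact be compared cannot be known from the documents.

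**What to change.** In section 6.1.5, the matching synopsis text and the SAP, replace the change in counts with the change from baseline in gout flare rate per observed patient-month:
- baseline rate = six-month count / 6;
- rate in each on-study interval = total flares / total observed patient-months in that interval;
- each interval compared with baseline in the same patients, with a 95% confidence interval.

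Also report the proportion of patients with at least one flare in Months 1-3 and in Months 4-6, so that it can be set beside the percentages in section 1.2.2. Define the two periods as equal in length (two 6-week intervals make 12 weeks, which a 13-week quarter would not match), and give the number of patients fully observed in each.

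A rate per observed time removes the window-length artefact. It does not deal with informative dropout, so the sensitivity analyses in section 6.1.5 are still needed.

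Separately, reconcile Schedule 2 of Appendix 3 with section 3.5.3 on flare assessment after early discontinuation.

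The cost is wording and minor programming. Flare occurrence is already to be recorded throughout the study, so no new assessment is added.

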### **1.2.1 Efficacy Assessments in Clinical Studies of KRYSTEXXA**

The safety and efficacy of KRYSTEXXA® (pegloticase) has been evaluated in 7 clinical studies, including 2 replicate, multicenter, randomized double-blind, placebo-controlled studies of 6-month duration. In the two placebo-controlled studies, adult patients with chronic gout refractory to conventional therapy were randomized to receive intravenous (i.v.) infusions of KRYSTEXXA 8 mg every 2 weeks or every 4 weeks or placebo in a 2:2:1 ratio. All patients also received prophylaxis for infusion reactions (IRs) and for gout flares. To assess the efficacy of KRYSTEXXA in lowering uric acid, the primary endpoint in both trials was the proportion of patients who achieved plasma uric acid (PUA) less than 6 mg/dL for at least 80% of the time during Month 3 and Month 6. A greater proportion of patients treated with KRYSTEXXA every 2 weeks achieved urate lowering to below 6 mg/dL than patients receiving placebo (38% to 47% of patients receiving KRYSTEXXA vs. 0% of patients receiving placebo). In addition, at Month 6, the percentage of patients who achieved a complete resolution of tophi (defined as 100% resolution of at least 1 target tophus, the appearance of no new tophi, and no single tophus showed progression) was 45%, 26% and 8% with KRYSTEXXA 8 mg every 2 weeks, KRYSTEXXA 8 mg every 4 weeks, and placebo, respectively. Although the 4 week regimen also demonstrated efficacy for the primary endpoint, this regimen was associated with an increased frequency of IRs and was less efficacious with respect to tophi. Therefore, pegloticase 8 mg every 2 weeks was approved by the US FDA on September 14, 2010 for the treatment of adult patients with chronic gout refractory to conventional therapy.

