### **3.5.2.2 Visits 13 and 26**

In addition to the study procedures listed for Visits 1 through 26, the following assessments will also be collected at 6 months (Visit 13) and 12 months (Visit 26) after initiating treatment with KRYSTEXXA:

- Perform swollen joint and tender joint counts
- Perform a count of the total number of palpable subcutaneous and subperiosteal tophi, if accessible

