##### **3.6.2.3 Number of Tophi**

A count of the total number of palpable subcutaneous tophi will be performed at Baseline/Screening, at 6 months (Visit 13) and at 12 months (Visit 26) or Early Discontinuation.

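### The tophus endpoint is a count change in the synopsis but an undefined patient-level resolution in 6.1.5, and the counts described can only bound the Phase 3 measure

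*Protocol*

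**What the plan says.** **Endpoint.** The efficacy criteria in the protocol synopsis list "Reduction in the number of tophi". The synopsis statistical methods plan descriptive statistics "for change in the number of tophi at 6 months (Visit 13) and 12 months (Visit 26) or Early Discontinuation". Section 6.1.5, at the same time points, plans them "for elimination of tophi, i.e., the number of patients with a reported tophus resolution". All of this is current text.

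**Data.** Section 3.5.2.2 instructs sites: "Perform a count of the total number of palpable subcutaneous and subperiosteal tophi, if accessible". Sections 3.5.3 and 3.5.4 ask for the same count at early discontinuation, and section 3.5.1 includes it in the screening assessment. Section 3.6.2.3, which defines the efficacy assessment, says: "A count of the total number of palpable subcutaneous tophi will be performed". It leaves out subperiosteal tophi.

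**Comparison.** Section 6.1.5 states: "The resulting summarized statistics for efficacy will be compared to those reported from the pre-approval Phase 3 studies". The one Phase 3 tophus result in the documents is in section 1.2.1: complete resolution at Month 6 in 45% (every 2 weeks), 26% (every 4 weeks) and 8% (placebo), "defined as 100% resolution of at least 1 target tophus, the appearance of no new tophi, and no single tophus showed progression".

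**Denominator.** Section 6.1.2 makes the overall N the default for percentages unless the SAP says otherwise. The SAP says nothing about tophi. Its efficacy items refer only to a primary efficacy effect.

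**The concern.** A within-patient change in count and a yes/no outcome per patient are different endpoints, and the yes/no version is not defined. The word elimination suggests that no tophi remain, whereas a single reported resolution suggests that one has gone. For a patient with several tophi these can give opposite answers, so the reported rate would depend on a choice made at analysis, possibly after the data have been seen.

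The Phase 3 definition also uses facts about individual tophi: which were targets, whether any progressed, whether any were new. The follow-up described here records none of these. A rate from this study placed beside 45% could differ because of the definition, the denominator or the tophus types counted, with no difference in treatment effect.

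**Working it through.** The plan states no design figure for this endpoint, and the 45% cannot be recomputed because the documents give no denominator. The check is therefore what the counts can determine.

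**1. Do total counts fix the Phase 3 status?** Inputs: baseline count b (1 to 5); each baseline tophus resolved, present without progression, or progressed; 0 to 2 new tophi. Assumptions: every baseline tophus can be a target, and the same types are counted at both visits. Follow-up count = unresolved baseline tophi + new tophi. Phase 3 success = at least one resolved, none new, none progressed. Enumerating all combinations gives:

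| Follow-up count | Phase 3 status |
|---|---|
| 0 | met |
| above 0, below b (b = 2 to 5) | either |
| b or more | not met |

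Example, 3 falling to 2: one resolved and two stable meets the definition. One resolved, one progressed and one stable does not. Two resolved and one new does not.

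Among patients with at least one baseline tophus, therefore:

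- lower bound = share with follow-up count 0
- upper bound = share with any fall in count
- width = share with a count above 0 but below baseline

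A patient with one baseline tophus is never ambiguous.

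**2. How far apart can the two readings of resolution be?** The documents give neither baseline counts nor per-tophus resolution rates. As an illustration only, assume each tophus resolves with probability p = 0.2, k = 3 or 5 baseline tophi, no new tophi, and within-patient correlation ρ from 0 to 1.

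- ρ = 0: at least one = 1 − 0.8^k; all = 0.2^k.
- ρ = 0.5 (beta-binomial, a = 0.2, b = 0.8). For k = 5, at least one = 1 − (0.8·1.8·2.8·3.8·4.8)/120 = 1 − 0.613; all = (0.2·1.2·2.2·3.2·4.2)/120 = 0.059. For k = 3, at least one = 1 − (0.8·1.8·2.8)/6 = 1 − 0.672; all = (0.2·1.2·2.2)/6 = 0.088.
- ρ = 1: both equal p.

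| ρ | k = 3: at least one / all | k = 5: at least one / all |
|---|---|---|
| 0 | 48.8% / 0.8% | 67.2% / 0.03% |
| 0.5 | 32.8% / 8.8% | 38.7% / 5.9% |
| 1 | 20% / 20% | 20% / 20% |

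With no new tophi, these pairs are also the upper and lower bounds from step 1. Only the direction is certain: at least one is never less frequent than all.

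**3. Denominator.** If a fraction f of the analysed patients have a tophus at baseline and r is the rate among them, dividing by overall N reports f × r. The documents do not give f.

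**The case against.** Five points deserve weight.

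- A reader might infer that total counts yield nothing about resolution. That is too strong. Any fall in the count proves that at least one tophus resolved, and step 1 settles every patient at zero or at or above baseline. Only intermediate falls are ambiguous, although an unchanged count can hide one resolution offset by one new tophus.
- A reader might infer that individual tophi are definitely not recorded. The documents do not establish this. Section 3.5.1 asks for an assessment that includes a count, the Appendix 3 schedules say only tophus assessment, and the case report form is not available. What can be said is that the protocol describes only a total count at follow-up.
- A reader might infer that a comparison with 45% is planned by name. The sentence in 6.1.5 is general and names neither tophi nor a figure, and the SAP outline lists no such comparison. The 45% is the natural comparator because it is the only two-weekly Phase 3 tophus result given. That remains an inference.
- A reader might take the independence row of the table as the size of the problem. Tophi in one patient share the same urate response, so independence is implausible, and under full correlation the two readings agree.
- The endpoint belongs to a secondary objective, is one of four efficacy criteria and carries no hypothesis test.

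These points limit the size of the problem. They do not remove the conflict between the synopsis and 6.1.5, the undefined term, the mismatch in tophus types or the silence of the SAP.

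**Conclusion.** The tophus endpoint is inconsistent within the protocol, its patient-level form is undefined, and the SAP resolves neither. If every baseline tophus can be a target, the counts described bound the Phase 3 complete-resolution rate but do not reproduce it. The width of the bounds is the share of patients whose count falls without reaching zero, which cannot be estimated from the documents.

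Read literally, 6.1.2 dilutes the rate further by including patients with no baseline tophi. That rule sits under the section on demographic characteristics but is worded for all categorical data.

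No type I error rate, power or sample size is affected. This should be corrected before analysis, but it does not threaten the study's primary safety objective.

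**What to change.** 1. In the synopsis, section 6.1.5 and the SAP, define one tophus analysis: change in total tophus count, plus the proportion reaching zero, both among patients with at least one tophus at baseline. Remove the undefined resolution wording.
2. Count the same tophus types in section 3.5 and section 3.6.2.3.
3. Either label the Phase 3 tophus comparison as not like-for-like and give the zero-count and any-decrease proportions as lower and upper bounds, or drop it. If the case report form does record individual tophi, say so and define the outcome from those data.

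The cost is protocol and SAP wording, with no new visit or procedure. The downside is that one descriptive historical comparison is weakened or lost.
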